### **2.9.2 Benefits**

Trial participants will contribute significantly to the development of a safer smallpox vaccine, which is a benefit to society in view of a potential threat following deliberate release of smallpox virus. Based on the current immunogenicity and efficacy data collected for IMVAMUNE® in preclinical and clinical studies, trial participants (except the trial participants receiving placebo) are expected to acquire protection against smallpox infection.

Future analysis of the samples collected will not directly benefit the subject. BN may learn more about smallpox and other diseases: how to prevent them, how to treat them, or how to cure them.

## **3 Objectives**

Please refer to trial protocol synopsis (see [section 1.5](#)).

## 4 Trial Design

### 4.1 Experimental Design

This trial is a randomized, double-blind, placebo-controlled Phase III trial to evaluate immunogenicity and safety of three consecutive production lots of IMVAMUNE® (MVA-BN®) smallpox vaccine in healthy, vaccinia-naïve subjects.

In total, four thousand (4,000) vaccinia-naïve subjects will be enrolled in this trial. All subjects will be randomly assigned (1:1:1:1) to one of three IMVAMUNE® groups (Groups 1-3) or the placebo group (Group 4) to receive two vaccinations each with IMVAMUNE® or placebo administered in a double-blind manner.

- Group 1 1,000 subjects will receive two s.c. vaccinations with 0.5 ml IMVAMUNE® Lot 1
- Group 2 1,000 subjects will receive two s.c. vaccinations with 0.5 ml IMVAMUNE® Lot 2
- Group 3 1,000 subjects will receive two s.c. vaccinations with 0.5 ml IMVAMUNE® Lot 3
- Group 4 1,000 subjects will receive two s.c. vaccinations with 0.5 ml Placebo (TBS)

### 4.2 Description of Trial Procedures

The trial procedures will be conducted according to the [Trial Procedure Schedule \(section 1.6\)](#) and as described in this chapter. Visits should be scheduled within the given intervals / visit windows.

#### 4.2.1 Screening Phase

Screening Visit (Day -28 to -1)

All subjects must be thoroughly informed of all aspects of the trial (e.g. trial visit schedule, required evaluations and procedures, risks and benefits) as described in the informed consent form (ICF). The ICF must be reviewed with the subject and signed and dated by the subject and the investigator or person designated by the investigator who conducted the informed consent discussion prior to the initiation of any evaluations or procedures required by the protocol.

After informed consent has been collected, subjects will enter a screening period of up to 28 days before the first vaccination.

Screening Visit (Days -28 to -1)

The following tasks will be performed:
 

• Subject to read, sign and date ICF

• Check vaccination history (previous smallpox vaccination or vaccination with a pox-virus-based vaccine) and absence of smallpox vaccine scar

• Check for all inclusion/exclusion criteria

• Obtaining medical history and prior/concomitant medications

• Complete physical examination including auscultation of heart and lungs and measurement of body weight and height

- Evaluation of vital signs
- Evaluation of family cardiac risk factors
- Calculation of the individual cardiac risk factor (after receipt of lab results for cholesterol)
- Perform baseline ECG
- Counseling on avoidance of pregnancy: Review of acceptable contraceptive methods and recent menstrual history with WOCBP
- Blood draw for safety laboratory (11 ml) including
  - troponin I
  - serum pregnancy test (WOCBP only)
  - cholesterol (total, HDL and LDL)
- Recording and documentation of baseline signs and symptoms

If a subject is screened and cannot be enrolled, because of a certain transient condition (e.g. abnormal lab value due to an acute condition or a missing lab evaluation due to mishandling of the sample), then the subject can be re-screened and the respective test(s) should be repeated as a "partial" re-screening rather than a full re-screening. The re-screening visit must be within the 28 day window started by the first screening visit and the window -28 to -1 before 1st vaccination must not be exceeded. A "partial" re-screening visit is indicated by filling out only the respective re-screening sections of the electronic Case Report Form (eCRF).

If a subject can not be enrolled due to other circumstances (e.g. completion of a wash-out period for a medication or vaccine not allowed during the trial) and the 28 day period is over, a complete re-screening assessment including physical examination, lab examination, and ECG must be performed. The clock then re-starts at the re-screening visit with Day -28 before the first vaccination.

#### 4.2.2 Active Trial Phase

After successfully passing the screening assessments the eligible subject will enter the active trial phase (Visit 1 to Visit 5) starting with Visit 1.

Randomized treatment assignments for the subjects will be done at Visit 1 after re-confirmation of subject's eligibility. The randomization scheme is 1:1:1:1 (three IMVAMUNE® production lot groups and one placebo group). Randomization will be stratified by CTS. An automated randomization system will be used. The detailed process will be described in a trial specific charter.

The procedures performed at Visit 1 and all following visits are listed below. **Blood draws and all other examinations listed above the vaccination events must always be performed prior to vaccination.**

At Visit 1 / Day 0, subjects will receive the first of two s.c. vaccinations with one standard dose of IMVAMUNE® (0.5 ml vaccine containing a nominal titer of  $1 \times 10^8$  TCID50) or placebo containing TBS in the non-dominant upper arm (deltoid region).

Following vaccination, subjects will be kept under close observation by the CTS staff for at least 30 minutes with appropriate medical treatment readily available in case of an unexpected anaphylactic reaction following administration of the vaccine. Any AEs that occur during or after vaccination will be recorded.

Reactogenicity and AEs will be collected on a subject memory aid by having the subject record daily maximum temperatures and solicited AEs for an 8-day period (Days 0-7), beginning with the day of vaccination. The memory aid will be returned to the clinic staff at the following visit. If symptoms persist at Day 7, daily symptoms and temperature will continue to be measured each day until resolved and the last day of symptoms and maximum intensity is recorded on the memory aid. AEs will be assessed at all active trial period visits (Visit 1 to Visit 5).

Visit 1 (Day 0)

Task to be performed prior to randomization and vaccination:
 

• (Re-) Check of inclusion / exclusion criteria

• Targeted physical examination including auscultation of the heart and lungs

• Evaluation of vital signs

• Recording of concomitant medications

• Recording of baseline signs and symptoms and SAEs

• Counseling on avoidance of becoming pregnant: Review of acceptable contraceptive methods and recent menstrual history with WOCBP

• Urine pregnancy test (WOCBP only)

• Blood draw (serum collection, 8 ml) for baseline antibody analysis

 
Blood draw and all tasks mentioned above must always be performed prior to vaccination. If the subject is still eligible for participation in this trial the subject will be randomized. The following tasks will be performed after randomization:
 

• Administration of first trial vaccination (IMVAMUNE® or placebo s.c.).

• Handout of memory aid, ruler and thermometer

• Subject observation by CTS staff for at least 30 minutes after vaccination

• Recording of immediate AEs/ Adverse Events of Special Interest (AESIs)/SAEs

 
Temporary deferral of vaccination: If an acute illness is present, the subject may be vaccinated at a later date within the accepted time window. The vaccine can be administered to persons with a minor illness such as diarrhea, mild upper respiratory infection, or any other mild condition with or without low-grade febrile illness, i.e. oral temperature < 100.4°F (< 38.0°C).

**Visit 2 (Visit 1 + 12–16 days)**

**The following tasks will be performed:**

- Targeted physical examination including auscultation of the heart and lungs
- Evaluation of vital signs
- Examination of the injection site
- Performing ECG
- Collection of the memory aid handed out at Visit 1, review with subject
- Blood draw for safety laboratory ( 11 ml) including troponin I
- Recording of AEs/SAEs/AESI and concomitant medication

**Visit 3 (Visit 1 + 28–35 days)**

**Tasks to be performed prior to vaccination:**

- Check withdrawal criteria
- Targeted physical examination including auscultation of the heart and lungs
- Evaluation of vital signs
- Counseling on avoidance of becoming pregnant: Review of acceptable contraceptive methods and recent menstrual history with WOCBP
- Urine pregnancy test (WOCBP only)
- Recording of AEs/SAEs/AESIs and concomitant medications

**All tasks mentioned above must always be performed prior to vaccination.**

**The following tasks will be performed after vaccination:**

- Administration of second trial vaccination (IMVAMUNE® or placebo s.c.).
- Handout of memory aid
- Subject observation by CTS staff for at least 30 minutes after vaccination
- Recording of immediate AEs/AESIs/SAEs

**Temporary deferral of second vaccination:** If an acute illness is present, the subject may be vaccinated at a later date within the accepted time window. The vaccine can be administered to persons with a minor illness such as diarrhea, mild upper respiratory infection, or any other mild condition with or without low-grade febrile illness, i.e. oral temperature < 100.4°F (< 38.0°C).

**Visit 4 (Visit 3 + 12–16 days)**

**The following tasks will be performed:**

- Targeted physical examination including auscultation of the heart and lungs
- Evaluation of vital signs
- Examination of the injection site
- Perform ECG (if clinically indicated)
- Blood draw for safety laboratory (11 ml, including troponin I testing if clinically indicated)
- Blood draw (serum collection, 8 ml) for antibody analysis
- Recording of AEs/SAEs/AESIs and concomitant medications
- Collection of the Memory aid handed out at Visit 3, review with subject

**Visit 5 (Visit 3 + 28–35 days)**

- Targeted physical examination including auscultation of the heart and lungs
- Evaluation of vital signs
- Urine pregnancy test (WOCBP only)
- Recording of AEs/SAEs/AESIs and concomitant medications

**4.2.3 Follow-Up (FU) Phase**

To monitor long-term safety, the CTS will contact the subject by phone to inquire whether an SAE /AESI might have occurred since the last trial visit and if there is any new information on SAEs/AESIs/AEs ongoing at last trial visit. In cases where a serious condition is detected, the trial subject will be requested to return for a physical examination and further work-up at the CTS.

For subjects who were withdrawn from the 2nd vaccination, the FU visit will be performed 6 months after the 1st vaccination (see section 4.2.5. withdrawal from 2nd vaccination).

**Phone FU (Visit 3 + 182–210 days)**

- Recording of new SAEs/AESIs and follow-up on ongoing SAEs/AESIs/AEs

**If a physical visit at the CTS is deemed necessary, the following should be performed:**

- Targeted physical examination including auscultation of the heart and lungs
- Evaluation of vital signs
- Blood draw for safety laboratory (11ml), if required
- Other safety evaluations, if required

#### 4.2.4 **Unscheduled Visits**

If clinically indicated, additional visits may be necessary between scheduled visits. Unscheduled visits may be scheduled to repeat laboratory testing or physical exams due to a new development. Examinations, performed at unscheduled visits will be documented in the source documents as well as on the respective eCRF pages for unscheduled visits.

#### 4.2.5 **Withdrawal from Second Vaccination**

The decision not to administer the second vaccination can be made by the investigator or by the subject.

##### Criteria:

The following criteria should be checked prior to second vaccination. If any are applicable, the subject should not receive the second vaccination:

- Any clinically significant cardiac sign and symptom (i.e. AESI) defined in Section 8.1.3.3.
- An AE that, in the opinion of the investigator, makes it unsafe for the subject to receive the second vaccination. In this case, the appropriate measures will be taken.
- Anaphylactic reaction following the administration of any vaccine(s).
- Administration of a licensed vaccine not foreseen by the clinical trial protocol.
- Start of chronic administration (defined as more than 14 days) of > 5 mg prednisone (or equivalent) per day or any other immune-modifying drugs.
- Administration of immunoglobulins and/or any blood products.
- Clinical need for concomitant or ancillary therapy not permitted in the trial.
- Use of any investigational or non-registered drug or vaccine other than the trial vaccine.
- Any condition which contradicts administration of the second vaccination in the opinion of the investigator.
- Pregnancy.
- Subject refuses to receive second vaccination.

##### Procedure:

If the subject did not receive the second trial vaccination the reason for this decision must be recorded in the eCRF and in the subject's medical record. V3 and V4 are not required; and the procedures below should be followed:

- Visit 5 procedures have to be performed within 28 to 35 days after Visit 1.
- FU visit procedures have to be performed 182 to 210 days after Visit 1.

#### 4.2.6 **Premature Discontinuation**

The trial may be discontinued prematurely for a subject at any time. The decision to discontinue the trial for a subject prematurely can be made by the investigator as well as by the subject himself. Reasons for discontinuing the trial prematurely may include, but are not limited to the following:

Criteria:

- Subject's request to discontinue prematurely (withdrawal of informed consent).
- Subject unwilling or unable to comply with trial requirements.
- Any reason that, in the opinion of the investigator, precludes the subject's further participation in the trial.
- Discontinuation due to an AE.

Procedure:

If a subject discontinues prematurely, the reason for this decision must be recorded in the eCRF and in the subject's medical record. If the subject is unable or not willing to attend all planned visits, every attempt should be made to perform at least a concluding safety visit. For WOCBP a pregnancy test should be performed during this safety visit. If the subject is not willing to undergo any further trial procedure (withdrawal of consent), "withdrawal of consent" needs to be documented as reason for premature discontinuation.

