Secondary endpoints	
Immunogenicity
 
GMTs after two IMVAMUNE® vaccinations measured by Enzyme-linked Immunosorbent Assay (ELISA) at trial Visit 4.
 
PRNT and ELISA seroconversion rates at trial Visit 4.
 
Pearson Correlation Coefficient between the log10 transformed PRNT titers and the log10 transformed ELISA titers at trial Visit 4.
 
Safety and Reactogenicity
 
Occurrence, relationship and intensity of any Serious Adverse Event (SAE) at any time during the trial.
 
Occurrence, relationship and intensity of any cardiac sign or symptom indicating a case of myo-/pericarditis.
 
Occurrence of any Grade 3 or 4 adverse events (AEs) probably, possibly or definitely related to the trial vaccine within 28 days after vaccination.
 
Occurrence, relationship and intensity of unsolicited non-serious AEs within 28 days after each vaccination.
 
Occurrence, intensity and duration of solicited local AEs (redness, swelling, induration, pruritus and pain) during the 8-day period (day of vaccination and the following 7 days) after each vaccination.
 
Occurrence, relationship, intensity and duration of solicited general

---------------------	---

AEs (pyrexia, headache, myalgia, nausea, fatigue and chills) during the 8-day period (day of vaccination and the following 7 days) after each vaccination.

Trial design

Randomized, double-blind, placebo-controlled:

Group 1	1,000 subjects will receive two s.c. vaccinations with 0.5 ml IMVAMUNE ® Lot 1
Group 2	1,000 subjects will receive two s.c. vaccinations with 0.5 ml IMVAMUNE ® Lot 2
Group 3	1,000 subjects will receive two s.c. vaccinations with 0.5 ml IMVAMUNE ® Lot 3
Group 4	1,000 subjects will receive two s.c. vaccinations with 0.5 ml Placebo (TBS)

Visit Schedule:

Visit (V)	Day	Target Week	Vaccination
SCR	Day -28 to -1	-4	
V1	Day 0	0	X
V2	V1 +12 - 16	2	
V3	V1 +28 - 35	4	X
V4	V3 +12 - 16	6	
V5	V3 +28 - 35	8	
Phone FU	V3 +182 - 210	30	

Subject entry criteria

Inclusion criteria

1. Male and female subjects, 18 to 40 years of age
2. The subject has read, signed and dated the informed consent form, having been advised of the risks and benefits of the trial in a language understood by the subject and prior to performance of any trial specific procedures
3. BMI  $\geq$  18.5 and  $<$  35

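### Section 4.2.6 does not require the six-month SAE/AESI call for subjects who discontinue prematurely without withdrawing consent, although 4.2.5 requires it for subjects who only miss dose 2

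*Protocol*

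**What the plan says.** Section 4.2.6 (Premature Discontinuation) covers subjects who leave the trial early. Its non-exhaustive reasons include withdrawal of consent, non-compliance, investigator judgement and "Discontinuation due to an AE". The follow-up rule begins "If the subject is unable or not willing to attend all planned visits" and then asks that "every attempt should be made to perform at least a concluding safety visit". No date is set for that visit and no later contact is named. Refusal of every further procedure is treated separately, as withdrawal of consent.

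Section 4.2.5 (Withdrawal from Second Vaccination) covers subjects who do not receive dose 2. Its criteria include "An AE that, in the opinion of the investigator, makes it unsafe for the subject to receive the second vaccination" and "Any clinically significant cardiac sign and symptom (i.e. AESI) defined in Section 8.1.3.3". For these subjects Visit 5 procedures take place 28 to 35 days after Visit 1, and "FU visit procedures have to be performed 182 to 210 days after Visit 1". Section 4.2.3 repeats the six-month follow-up for this group.

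The synopsis (section 1.5) lists as a secondary safety endpoint "Occurrence, relationship and intensity of any Serious Adverse Event (SAE) at any time during the trial". Its myo-/pericarditis endpoint carries no time limit. Under section 9.4 the Full Analysis Set needs one dose and some post-vaccination safety data; completing follow-up is not a condition.

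**The concern.** After Visit 5 the phone contact is the only scheduled point at which the site asks every subject about new SAEs and AESIs. A subject who misses dose 2 and stays in the trial is owed that contact. A subject who discontinues under 4.2.6 is owed one undated visit, even if willing to take a call.

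Two groups are affected. A subject with an adverse event after dose 1 can meet the wording of both sections, which require different follow-up, and no rule says which governs. A subject who stops after dose 2 cannot come under 4.2.5 at all.

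At stake is the completeness of late safety data. An event that nobody asks about is counted as no event, while the subject remains in the denominator. This matters in a trial that enlarges its arms for safety and plans to draw conclusions from zero, one or two cases of myo-/pericarditis.

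**Working it through.** **1. The provisions side by side**

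| | 4.2.5, dose 2 not given | 4.2.6, premature discontinuation |
|---|---|---|
| Adverse event as a reason | yes | yes |
| Applies after dose 2 | no | yes |
| Last clinic visit | 28–35 days after Visit 1 | concluding visit, undated |
| Contact at 182–210 days | required | not mentioned |

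Sections 8.2.5 and 8.2.7 follow ongoing SAEs and AESIs until they resolve or stabilise, with no exception for discontinued subjects. The event that led to stopping is therefore covered. Section 4.2.3 dates the general phone contact from Visit 3 and adapts it only for subjects withdrawn from dose 2. What lacks an explicit rule is active inquiry about new events after a 4.2.6 departure.

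**2. The plan's own safety figure**

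Section 9.3 claims a 95% chance of detecting an event of incidence 1/1,000 in 3,000 vaccinees: 1 − (1 − 0.001)^3000 = 0.9503. This reproduces. The one-sided 95% upper limit with zero cases is 1 − 0.05^(1/3000), or 1/1,002, which supports the plan's statement of a rate below 1/1,000.

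**3. Person-time that could go unobserved**

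Inputs, at the midpoints of the protocol windows:
- Visit 3 falls at (28 + 35)/2 = 31.5 days after Visit 1.
- The phone contact falls at (182 + 210)/2 = 196 days after the last vaccination.
- Planned follow-up of a two-dose subject is 31.5 + 196 = 227.5 days. For 3,000 vaccinees this is 3,000 × 227.5 / 365.25 = 1,869 person-years.
- Assumption: the subject leaves 28 days after dose 1, so a call dated from that dose would have added 196 − 28 = 168 days.

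The share leaving under 4.2.6 is not in the protocol and is varied:
- 5%: 150 × 168 / 365.25 = 69 person-years; 69/1,869 = 3.7%.
- 15%: 450 × 168 / 365.25 = 207 person-years; 207/1,869 = 11.1%.

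Timing matters less than the share. A subject who leaves right after a dose loses up to 196 days, which gives 0.05 × 196/227.5 = 4.3% and 0.15 × 196/227.5 = 12.9%.

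The 15% comes from section 9.3, where it supports testing 700 samples per group to obtain 600 in the per-protocol set. It is not a rate of lost six-month contact. It may include subjects who missed dose 2 and keep the call, and consent withdrawals that no rule can recover.

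**4. Extreme case for the counting statements**

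Suppose lost subjects contributed nothing at all. This overstates the loss, since they are observed until they leave.

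| Share lost | N | Detection at 1/1,000 | Zero-case upper limit |
|---|---|---|---|
| 0% | 3,000 | 95.0% | 1/1,002 |
| 5% | 2,850 | 94.2% | 1/952 |
| 15% | 2,550 | 92.2% | 1/852 |

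The zero-case statement has little slack. It needs N of at least ln(0.05)/ln(0.999) = 2,994.2, that is 2,995 subjects. The comparison with 1/330 is robust: with two cases, P(X ≤ 2) at a rate of 1/330 is 0.0057 for N = 3,000 and 0.017 for N = 2,550.

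**The case against.** Several counter-arguments have force.

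- **The concluding visit is a minimum.** A reader might infer that follow-up ends there by rule. The text does not say so: the wording is a floor for subjects who will not attend everything, and nothing forbids a later call. Section 4.2.3 also states the phone contact generally, without excepting discontinued subjects. This stands. The defect is that the call is not required in 4.2.6, not that it is barred.
- **Section 4.2.5 turns on a fact, non-receipt of dose 2.** A subject barred from dose 2 by an adverse event or a cardiac sign, or who refuses it, keeps the call if still in the trial. This stands and narrows the overlap. It does not settle the case of a subject who discontinues the trial because of that event, and it does not reach anyone who stops after dose 2.
- **Loss concentrated in subjects who stop for an adverse event, with bias towards safety.** A reader might infer this, because local and some general reactions are very common on the vaccine. The documents do not support it as a finding: 4.2.6 treats every reason alike, ongoing SAEs and AESIs are followed, and no discontinuation rate by reason or arm is given.
- **Late events can still be reported.** Sections 8.3.1 and 8.3.2 require reporting of all SAEs and AESIs the site learns of throughout the trial, and 4.2.4 allows unscheduled visits. This stands, but it depends on the subject coming forward.
- **Late person-time is a weak measure for myo-/pericarditis,** because section 9.3 places cardiac monitoring two weeks after each administration. This also stands. The gap bears mainly on late SAEs.

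**Conclusion.** The gap is real but limited. Followed as written, 4.2.6 does not require that new SAEs and AESIs be actively sought after an undated concluding visit, even in subjects who have not withdrawn consent to contact. Those subjects remain in the Full Analysis Set, and the SAE endpoint runs for the whole trial. Section 4.2.5 shows that the sponsor wanted the six-month contact for subjects with incomplete vaccination.

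The size cannot be fixed from the protocol. About 4% of planned vaccinee person-time at 5% discontinuation is an illustration. About 11% at 15% is best read as a ceiling on the share leaving, because the 15% is an immunogenicity dropout figure. Both assume departure about four weeks after dose 1. Difference between arms is possible but not shown, and the comparison with 1/330 is not threatened. The point merits correction because late safety ascertainment can be improved at little cost.

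**What to change.** In 4.2.3 and 4.2.6, state that every vaccinated subject who has not withdrawn consent to be contacted receives the SAE/AESI phone follow-up 182 to 210 days after the last vaccination received. This also gives a defined call date to subjects who leave before Visit 3. Reconcile 4.2.5 and 4.2.6 so that sites know which applies when an adverse event meets both; which one should govern is for the sponsor and investigators to decide.

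The cost is protocol wording, a consent sentence that separates stopping visits from refusing contact, and extra effort to reach discontinued subjects by phone. No new assessments are needed, and the call is already part of the planned schedule.
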